- Participants will complete the same questionnaires about sleep quality, anxiety, and depression symptoms, and menopausal quality of life that they completed at baseline.
- Participants will be asked to wean off NTG (or placebo) over the next 1 to 3 days, by decreasing their patch dose on a nightly basis before stopping NTG/placebo completely. Women will be given a last supply of NTG or placebo medication to complete the weaning.
- Once weaning is complete, participants will be instructed to avoid using any NTG or nitrate products until after the post-discontinuation telephone call.
- A participant satisfaction questionnaire will be administered.

G. 4-Week Post-Discontinuation Telephone Call

- At least 28 days after the 12-Week Clinic Visit or after the participant discontinues study medication, study coordinators will contact participants by telephone.
- Potentially severe side effects of NTG will be systematically assessed and recorded by phone, and other reported adverse events will also be documented according to standard protocols.
- At the participant's request, or if there is a safety concern, this telephone call can be converted to an in-person visit.

H.2.6 Early termination

If a randomized participant opts to terminate the study before the 12-Week Clinic Visit, or if the principal investigator in consultation with the Data and Safety Monitoring Board determines that early termination is necessary to protect the safety of a participant or the integrity of the study, the study coordinator will encourage the participant to complete an early termination visit. This visit will include as many of the procedures originally scheduled to take place at the 12-Week Clinic Visit as possible, including: completion of a final hot flash diary; assessment of adverse events; re-administration of questionnaires about sleep quality, anxiety and depression symptoms, and condition-specific quality of life; review of current medications; re-assessment of weight, blood pressure, and heart rate; and administration of a satisfaction questionnaire. Study staff will provide instructions for weaning off NTG (or placebo) medication, and provide additional patches needed to complete the weaning. The participant's reasons for terminating the study early will be explored and documented in her study file.

H.2.7 Adherence to procedures and visits

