Every effort will be made to assure that participants complete follow-up procedures and visits according to the study protocol. Participant contact information including address, phone number(s), fax number(s), and email address will be obtained at the Screening Clinic Visit. Study coordinators will also request contact information for two family members or friends who will be able to locate the participant. The study team will encourage retention by educating participants about the importance of the study, maintaining a friendly and efficient study clinic environment, and encouraging excellent staff-participant rapport. Participants who miss a visit will be contacted by the study coordinator to reschedule the visit and to provide assistance in completing the visit. Participants will also be offered gift cards with the return of each completed hot flash diary (\$25 at the Baseline Clinic Visit and 5-Week Clinic Visit, and \$50 at the 12-Week Clinic Visit).

H.2.8 Follow-up visit time windows

Suggested time windows for completion each of the post-randomization follow-up evaluations will be as follows:

| Follow-Up Assessment | Time Window |
|----------------------|-------------|
|----------------------|-------------|

| | |
|--|--|
| 1-week clinic visit | 7 (\pm 3) days after the baseline clinic visit (i.e., 4 to 10 days after the baseline visit) |
| 2-week clinic visit | 14 (\pm 3) days after the baseline clinic visit (i.e., 11 to 17 days after the baseline visit) |
| 3-week telephone call | 21 (\pm 3) days after the baseline clinic visit (i.e., 18 to 24 days after the baseline visit) |
| 5-week clinic visit | 5 weeks (\pm 6 days) after the baseline clinic visit (i.e., 29 to 41 days after the baseline visit) |
| 8-week telephone call | 8 weeks (\pm 6 days) after the baseline clinic visit (i.e., 49 to 63 days after the baseline visit) |
| 12-week clinic visit | 12 weeks (\pm 6 days) after the baseline clinic visit (i.e., 78 to 90 days after the baseline clinic visit) |
| 4-week post-discontinuation telephone call | 28 to 42 days after the 12-week clinic visit (or discontinuation of study medication) |

I. SAFETY ASSESSMENTS

I.1 Potential Risks and Protective Measures

I.1.1 Potential risks of study procedures

A. Potential risks associated with the therapeutic intervention (transdermal NTG) include:

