Hypertension: Potential participants will undergo measurement of blood pressure at both the screening and baseline visits, and those with blood pressure $>180/110$ at baseline will be excluded from the study due to the theoretical risk of increased blood pressure with induction of nitrate cross-tolerance. (Women may still seek further anti-hypertension therapy from their regular sources of health care and re-present for screening if desired). At all on-treatment interim follow-up visits (i.e., 1-week, 2-week, 5-week), blood pressure will be reassessed, and transdermal NTG will be decreased or stopped in women with blood pressures $>180/110$ mm Hg. Women with blood pressure $>180/110$ at any study visit will also be urged to seek emergency medical attention. Additionally, women with blood pressures $>160/100$ will be given a standardized letter to take to their regular health care provider to promote further evaluation and/or treatment. In the event that there is a concern about the reliability of clinic measurements, or women report high blood pressure measurements obtained elsewhere despite having blood pressure measurements in the normal range at their study visits, home-based or ambulatory blood pressure measurements may be obtained, to detect uncontrolled hypertension that may have been missed by in the study clinic. At the end of the treatment period, participants will be weaned off study medication rather than discontinuing medication abruptly, to minimize any risk of rebound hypertension.

Skin irritation: Women with known allergy to adhesives will be excluded, as these women may have a more significant reaction to the adhesive associated with the transdermal NTG patch. Women will also be advised to rotate the location of the patch on a nightly basis to minimize risk of skin reaction or breakdown. During the brief run-in period with the 0.1 mg/hr NTG patch, women who are unable to tolerate the patch will be excluded. If women subsequently develop significant skin irritation in response to using the transdermal nitrate (or placebo) patch, their participation in the study will be terminated early.

B. Protections against potential risks associated with other study data collection procedures:

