Study medication may be discontinued if deemed necessary to protect the safety of a participant or preserve the integrity of the study. The decision to discontinue study medication will be made on a case-by-case by the principal investigator, with input from the steering committee and the DSMB as needed. In most cases, discontinuation of study medication will prompt early termination of study participation, although there may be select cases where study medications are discontinued only temporarily, and the participant is subsequently restarted on study medication and then followed for the full duration of the study.

Specific reasons for discontinuation of study medication and/or early termination of the study include: 1) syncopal episode attributable to NTG-induced hypotension or vasodilation; 2) development of persistent blood pressure <90/60, blood pressure <100/60 with symptoms of dizziness, or orthostatic blood pressure with symptoms of dizziness, which do not resolve with reduction in study medication dose; 3) development of persistent severe hypertension defined by blood pressure >180/110; 4) development of pregnancy or decision to try to become pregnant (among women who are not yet postmenopausal); 5) development of another clinically significant adverse event limiting a participant's ability to safely continue to use the study drug; 6) unusually disruptive behavior exhibited by a participant during study visits that endangers the safety or well-being of the participant or study staff; or 7) decision to terminate the study by the IRB, the NIA, or other regulatory bodies.

Participants may also withdraw voluntarily from participation in the study at any time and for any reason. If a participant decides to discontinue the study drug or withdraw from the study, the study coordinator will try to elicit the reason for this decision. The coordinator may also try to trouble-shoot participant concerns or discuss strategies for overcoming barriers to continued participation in the study in order to try to retain the participant, provided that the decision to terminate is not driven by a safety issue.

J.2 Discontinuation/Termination Procedures

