In the event that study medication is discontinued early, study coordinators will attempt to schedule an early termination visit to collect outcomes data, provided that the participant is willing, and provided that the principal investigator (with input from the steering committee and DSMB as appropriate) judges that it is safe and feasible to do so.

This visit will include as many of the procedures originally scheduled to take place at the 12-Week Clinic Visit as possible, such as: completion of a final hot flash diary; assessment of adverse events; re-administration of other symptom and quality-of-life questionnaires; review of current medications; re-assessment of weight, blood pressure, and heart rate; and administration of a satisfaction questionnaire.

Regardless of whether the participant is able to complete an early termination visit, the study coordinator will document the reason for early termination in the participant's file, except in cases where a participant is lost to follow-up or declines to provide a reason for deciding to discontinuing participant early.

Upon study termination, participants will be asked to wean off NTG (or placebo) over the next 1 to 3 days, by decreasing their patch dose on a nightly basis before stopping NTG/placebo completely. Specifically, participants who are being weaned from the 0.6 mg dose of study medication will be instructed to switch to 0.4 mg for one day, then to 0.2 mg for one day, then to stop study drug altogether. Participants who are being weaned from the 0.4 mg dose will switch to 0.2 mg for one day before stopping medication altogether. Women who are taking the 0.2 mg (the lowest dose hypothesized to have a therapeutic effect) will simply stop study medication without any change in dose. Participant and staff blinding will be maintained throughout the weaning process; for participants taking placebo, weaning will use placebo rather than active NTG patches. If necessary, women will be given a last supply of NTG or placebo medication (one patch of each dose strength needed to complete the weaning).

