In the event that a participant develops a potentially severe adverse event such as chest pain during weaning, she will be directed to seek immediate emergency attention, just as she would during any other time point of the study. Although all study medication will be stopped while the participant receives emergency care, it should be possible to manage any side effects safely in the emergency care setting regardless of medication discontinuation.

Study coordinators will also try to schedule and complete a post-discontinuation telephone call that will occur at least 28 days after discontinuation of study medication, to promote appropriate monitoring of adverse events following discontinuation of study drug.

K. STATISTICAL CONSIDERATIONS

K.1 General Design Issues

A randomized, parallel-group, placebo-controlled trial design has been selected to examine the following aims and test the following hypotheses related to the efficacy, safety, and tolerability of transdermal NTG for treatment of menopausal hot flashes:

Objective 1: Determine the efficacy of uninterrupted transdermal NTG therapy in reducing the frequency of hot flashes in peri- and postmenopausal women.

Hypothesis 1: Compared to placebo, uninterrupted use of NTG will result in at least a 20% greater decrease in the frequency of hot flashes (measured by validated symptom diaries) over 12 weeks.

Objective 2: To evaluate the efficacy of uninterrupted transdermal NTG therapy in reducing the severity of hot flashes in peri- and postmenopausal women.

Hypothesis 2: Compared to placebo, uninterrupted use of NTG will result in significant improvements in frequency of moderate-to-severe hot flashes and in cumulative hot flash severity score (assessed by validated symptom diaries) over 12 weeks.

Objective 3: Evaluate the efficacy of uninterrupted transdermal NTG therapy in improving other symptom- and quality-of-life outcome associated with hot flashes in peri- and postmenopausal women.

Hypothesis 3: Compared to placebo, uninterrupted use of NTG will result in significant improvements in hot flash-related sleep quality, anxiety and depression, and menopause-related quality of life over 12 weeks.

Objective 4: Examine the tolerability and safety of uninterrupted transdermal NTG therapy in peri- and postmenopausal women with hot flashes.

Hypothesis 4: Compared to placebo, uninterrupted use of NTG will be associated with higher rates of mild

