headache during the first 24 hours of therapy, but no significant differences in rates of chest pain, syncope, or severe adverse events defined by CTCAE severity grade 3 or higher.

K.2 Data Analyses

K.2.1 Analyses for Objective 1

Analyses to address aim 1 will examine change in average daily hot flash frequency from baseline to 4 and 12 weeks of treatment, measured over 7 days by validated hot flash diaries (Sloan, Loprinzi et al. 2001, Food and Drug Administration 2003). The effect of NTG therapy will be estimated using linear mixed models (LMMs) for the repeated changes, adjusting for baseline values, under the assumption of an approximately constant treatment effects at 4 and 12 weeks; in supplementary analysis we will assess evidence for differences in the treatment effects at these two time points. The distribution of the LMM residuals will be assessed using Q-Q plots, and outcomes will be transformed if necessary to achieve approximate normality. Analyses will be by intention to treat, according to treatment assignment, and without regard to adherence.

K.2.2 Analyses for Objective 2

For additional confirmation of treatment effects on frequency of any hot flashes, we will also assess treatment effects on moderate-to-severe hot flashes and on total hot flash severity scores as secondary outcomes, also assessed by diary, using the same methods. The distribution of the LMM residuals will again be assessed using Q-Q plots, and outcomes will be transformed if necessary to achieve approximate normality. Analyses will again be by intention to treat, according to treatment assignment, and without regard to adherence.

K.2.3 Analyses for Objective 3

Analyses to address aim 2 will examine changes in sleep quality and duration, anxiety and depressive symptoms, and menopausal quality-of-life from baseline to 4 and 12 weeks. These outcomes will be captured by scores on validated self-administered questionnaires, with supplementation by sleep diary in the case of sleep duration. Intervention effects on these outcomes will be estimated using LMMs, adjusted for baseline scores. Approximate normality of the residuals will be checked using Q-Q plots, and outcomes will be transformed if necessary. Analyses will once again be by intention to treat and without regard to adherence.

K.2.4 Analyses for Objective 4

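### Stopping the patch for good usually ends outcome collection, although the primary analysis is promised as intention to treat regardless of adherence

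*Combined protocol and SAP*

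**What the plan says.** K.2.1 commits the primary analysis to this principle: "Analyses will be by intention to treat, according to treatment assignment, and without regard to adherence". Women who miss patches or stay on a lower dose remain in the study (F.1.6, I.1.2, L.3.3).

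Permanent stopping is handled differently. J.1 says: "In most cases, discontinuation of study medication will prompt early termination of study participation". Its only stated exception is a temporary stop followed by a restart. For significant skin irritation, I.1.2 says of these women that "their participation in the study will be terminated early".

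Four other provisions bear on the point:

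- **Early-termination visit (H.2.6, J.2).** Under H.2.6, "the study coordinator will encourage the participant to complete an early termination visit", including a final hot flash diary. J.2 makes the attempt conditional on her willingness and on the investigator, who "judges that it is safe and feasible to do so".
- **Later call (J.2).** This is a "post-discontinuation telephone call that will occur at least 28 days after discontinuation of study medication, to promote appropriate monitoring of adverse events". Appendix A lists no diary for it.
- **Retention (H.2.7, J.1).** H.2.7 is general: "Every effort will be made to assure that participants complete follow-up procedures and visits according to the study protocol". J.1 lets the coordinator address a woman's concerns "in order to try to retain the participant, provided that the decision to terminate is not driven by a safety issue".
- **Missing data (K.4.1).** Non-informative dropout is to be examined by comparing lost and retained women. Covariate adjustment follows only if dropout differs substantially between arms. Multiple imputation under informative missingness is a sensitivity analysis, and its scenarios are not given.

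**The concern.** An analysis regardless of adherence needs outcomes from women who no longer adhere. Here the women whose adherence ends altogether are the ones whose scheduled diaries normally stop. The mixed model then fills the gap implicitly from women still on the patch in the same arm.

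That is doubtful when stopping is linked to treatment. J.1 lists syncope attributable to NTG and unresolved low blood pressure among the reasons for stopping, and in the pilot (C.3) hot flash frequency rose 23% in the week after NTG was withdrawn. If NTG works and stoppers lose some of the effect, the estimate moves towards the effect of staying on the patch and away from the effect of being assigned to it.

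Equal stopping in the two arms does not prevent this, because placebo stoppers have no drug effect to lose. The K.4.1 trigger, a between-arm difference in dropout, can therefore miss it. The K.4.1 comparison of lost and retained women uses only observed data and cannot show what happened after stopping.

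**Working it through.** **1. The plan's power figure.** Inputs from K.3: 70 per arm, 15% loss (70 × 0.85 = 59.5 per arm), difference 1.8/day, SD of change 4.5, correlation 0.55, two-sided 5%. The correlation between the two follow-ups is not given; 0.55 is assumed.

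- SD of a single value: 4.5 / √(2 × 0.45) = 4.74.
- Residual SD of the mean of two follow-ups, adjusted for baseline: 4.74 × √((1 + 0.55)/2 − 0.55²) = 3.26. Power is 85.3%.
- With 4.5 itself taken as the SD of a value: residual SD 3.09, power 88.8%.

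These bracket the stated 87%, so the inputs are a fair basis for what follows.

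**2. Effect if everyone is followed.** Assume a share p of NTG women stop, half of them before the 5-week diary, and lose a share L of the 1.8/day. Averaged over the two visits, 0.75p of the NTG diaries are off drug:

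effect = 1.8 × (1 − L × 0.75p)

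For example, L = 0.5 and p = 0.15 gives 1.8 × (1 − 0.05625) = 1.699.

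**3. Effect that the plan would estimate.** Trials of 70 per arm were simulated with the values above (raw SD 4.74, all correlations 0.55, 2,000–4,000 replicates). Change was analysed with a constant effect and baseline adjustment by generalised least squares. Placebo stops were 5%. With post-stop diaries missing, the estimate stays at about 1.8. The overstatement is the difference from step 2, per day:

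| NTG stops | 10% | 15% | 25% |
|---|---|---|---|
| Half lost: effect if all followed | 1.733 | 1.699 | 1.631 |
| Half lost, no termination diary | 0.07 (4%) | 0.10 (6%) | 0.17 (10%) |
| Half lost, 70% give a diary off drug | 0.03 | 0.04 | 0.07 |
| Half lost, 70% give a diary on drug | 0.07 | 0.10 | 0.17 |
| 21% lost, no termination diary | 0.03 (2%) | 0.04 (2%) | 0.07 (4%) |
| All lost: effect if all followed | 1.665 | 1.598 | 1.463 |
| All lost, no termination diary | 0.14 (8%) | 0.20 (13%) | 0.34 (23%) |
| All lost, 70% give a diary off drug | 0.06 | 0.09 | 0.13 |

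The standard error is 0.57 to 0.59. Termination diaries were entered as the next scheduled value, since the plan gives no rule.

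**4. Where the 21% comes from.** In the pilot, frequency fell from 10.6 to 5.0 per day, a fall of 5.6. If the 23% rise is on a base of 5.0 (the base is not stated), the rebound is 1.15/day, and 1.15/5.6 = 21%. If 3/day of the fall is non-specific (the K.3 control-arm figure applied to the pilot), it is 1.15/2.6 = 44%. Both describe only one week off drug.

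**5. Other cases.**

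- *Equal stops, 15% in each arm, all effect lost:* 1.81 against 1.61, still 0.20 too high.
- *Reversed:* 15% of placebo women leave with no improvement and 5% of NTG women stop. The plan estimates 1.98 against 2.20, 0.22 too low.
- *No true effect, 25% against 5% stops:* bias 0.00, rejection rate about 5%.

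**The case against.** The strongest reply is that the effect is small. At 15% NTG stops the overstatement is 0.04 to 0.10 per day for 21% to half of the effect lost, under 0.2 standard errors. Stopping may also be rarer than assumed: the run-in removes women who cannot tolerate 0.1 mg/hr, and none of the 17 pilot women who tolerated that dose stopped for side effects. The 25%/5% case averages 15% and so uses up the whole dropout allowance on its own. All of this stands, though 0 of 17 is compatible with a true rate of up to about 16% (1 − 0.05^(1/17)), over 4 weeks rather than 12.

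The second reply is that the plan already does much of this. It tries for a termination diary, women who stop after the 5-week visit have given that diary, and K.4.1 commits to imputation under informative missingness. The reliance on non-informative dropout is therefore confined to the primary model and to the diaries that are missing. That too stands. But a termination diary helps only if recorded off drug, and the plan does not say when it is recorded or how it is analysed.

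Third, full follow-up is not attainable. If only 70% of stoppers return the later diaries, the half-loss gap at 15%/5% falls from 0.10 to about 0.03, against 0.04 with a 70% off-drug termination diary. The gain over a well-timed termination diary is thus about 0.01 per day. It is about 0.07 if that diary would have been recorded on drug.

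**Conclusion.** The concern holds. The gap in the text is certain: permanent stopping normally ends participation, and nothing asks these women for the scheduled diaries on which the intention-to-treat analysis depends. The consequence is probably modest, from a few hundredths to about 0.2 hot flashes per day, and reaches 0.34 only with 25% stopping, complete loss of effect and no termination diary. Stop rates by arm, loss of effect and diary return are assumptions; the documents give only dropout under 15% overall. Overstatement is the likelier direction if stopping is driven by NTG side effects; departures from placebo for lack of benefit could reverse it. The stated power is not wrong, and a false positive is not made more likely by side-effect stopping. It should be fixed because the remedy is cheap and diaries not collected cannot be recovered.

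**What to change.** **Protocol (J.1, J.2, H.2.6, I.1.2).** Separate stopping the patch from leaving the study. Ask a woman who stops to complete the remaining 5-week and 12-week diaries and questionnaires remotely, under the condition J.2 already sets: she is willing and the investigator judges it safe and feasible. Exempt withdrawal of consent, termination of the whole study, and conduct that makes follow-up unsafe. Record any hot flash treatment started after stopping. State when the early-termination diary is recorded, and use it only where later diaries are refused. The reasons and rules for stopping treatment stay as they are.

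**Analysis (K.2.1, K.4.1).** Analyse post-stop diaries as observed, under the assigned arm, with a sensitivity analysis for later hot flash treatment. For stoppers still missing, pre-specify reference-based (placebo-arm) or delta imputation.

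**Cost.** This takes a protocol amendment and up to two remote diary collections per stopper. Remote platforms are already foreseen (E.3, criterion 19), and stoppers are already to be called at 28 days or later.

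The estimate will probably be somewhat smaller. With all followed, power goes from about 88% to 87% (15%/5% stops) and from 87% to 84% (25%/5%) if half the effect is lost; if all is lost, it falls to about 81–82% and 74–75%.

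Treatments started after stopping will mix in, since F.2.2 restricts them only during the treatment period. If 30% of stoppers start one worth 1.8/day (assumption), the estimate rises by 0.3 × 1.8 × 0.75 × 0.10 = 0.04/day at 15%/5% and by 0.08 at 25%/5%. At 60% uptake it rises by 0.08 and 0.16.

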Headache: Potential side effects of NTG therapy are related to the medication's vasodilatory action. The most commonly reported side effect is headache, occurring most frequently in the first 24 hours of administration (Tfelt-Hansen and Tfelt-Hansen 2009). In previous placebo-controlled trials of intermittent therapy with transdermal NTG (in which the NTG patch was removed at bedtime and replaced the next morning) at 0.2 to 0.8 mg/hr, approximately 60% of participants taking transdermal NTG reported headache, compared to 18% of participants taking placebo (Rossouw, Prentice et al. 2007). Among persons using continuous transdermal nitrate (immediately replacing the old patch with a new patch), development of tolerance to the vasodilatory effects of transdermal nitrate is expected within 12 to 24 hours, which should diminish the frequency and severity of headache. In the study team's prior pilot trial of continuous NTG for treatment of hot flashes in peri- and postmenopausal women, 37% of participants reported headache at some point during the 6-week study but the average duration of headache was less than 24 hours.

Lightheadedness/hypotension: Lightheadedness has been reported with initiation of NTG therapy, presumably due to lowering of blood pressure during the first 12 to 24 hours of administration. In prior placebo-controlled trials of intermittent NTG therapy for other indications, 6% of participants taking transdermal NTG reported transient lightheadedness thought to be associated with lowering of blood pressure, compared to 4% of participants taking placebo (Rossouw, Prentice et al. 2007). It is possible but uncommon for patients using transdermal NTG patches to develop hypotension severe enough to cause syncope. In the case of hypotension, removal of the transdermal patch should result in immediate (within seconds to minutes) normalization of blood pressure. Any lightheadedness or lowering of blood pressure associated with transdermal NTG therapy should

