At all on-treatment interim follow-up visits (i.e., 1-week, 2-week, 5-week), transdermal NTG will be decreased or stopped in women with blood pressures <90/60 mm Hg (both measurements), or in those with blood pressures <100/60 mm Hg and symptoms such as dizziness that are suggestive of hypotension. Study medication will also be decreased or stopped in women with symptoms such as dizziness who have a resting blood pressure in the normal range but demonstrate orthostatic changes in blood pressure or heart rate when rising from the supine to standing position. These

women will also be given a standardized letter documenting their blood pressure reading to take to their regular health care provider to promote further monitoring and/or evaluation. In the event that there is a concern about the reliability of clinic measurements, or women report symptoms suggestive of hypotension despite having blood pressure measurements in the normal range, home-based or ambulatory blood pressure measurements will be obtained, to detect episodes of hypotension that may have been missed by clinic measurements. In the (hopefully unlikely) event that a participant reports a recent episode of syncope or loss of consciousness, study staff will also urge the participant to seek emergency medical attention.

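### The step-down on termination makes no exception for women stopped because nitroglycerin (NTG) caused syncope or unresolved hypotension

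*Combined protocol and SAP*

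**What the plan says.** J.1 lists reasons for discontinuing study medication, ending participation, or both. Reason 1 is a "syncopal episode attributable to NTG-induced hypotension or vasodilation". Reason 2 covers persistently low blood pressure, or low or orthostatic readings with dizziness, "which do not resolve with reduction in study medication dose". J.1 adds that stopping the drug will usually lead to early termination.

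J.2 then gives the procedure: "Upon study termination, participants will be asked to wean off NTG (or placebo) over the next 1 to 3 days". From 0.6 mg/hr the steps are one day at 0.4, one day at 0.2, then stop. From 0.4 they are one day at 0.2, then stop. Women on 0.2 stop at once.

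H.2.6 covers early termination, whether the participant chooses it or it is needed for her safety or for study integrity. It says: "Study staff will provide instructions for weaning off NTG (or placebo) medication, and provide additional patches needed to complete the weaning".

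On the remedy for hypotension, I.1.1 says that "removal of the transdermal patch should result in immediate (within seconds to minutes) normalization of blood pressure".

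**The concern.** The step-down is written as one rule for every termination. Its stated purpose, in I.1.2, is to limit rebound chest pain and rebound hypertension. That purpose does not fit a woman whose reason for stopping is that NTG lowered her blood pressure or made her faint. For her, the protocol's own remedy is to take the patch off, while its termination procedure asks her to put on another. Coordinators give the instructions and supply the patches, so the written rule matters even if a clinician would act differently. At stake is a short, avoidable exposure in a few women. No efficacy or safety analysis depends on it.

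**Working it through.** No statistical figure is involved. The check has two parts: whether any passage supplies the exception, and how much further patch use the rule implies.

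**Search for an exception**

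- *F.1.7 (end of treatment), H.2.6 and J.2:* steps are set by dose or simply required. None is conditional on the reason for stopping.
- *J.2, early termination visit:* this visit is subject to the principal investigator judging it safe and feasible. The weaning paragraph in the same section has no such condition.
- *I.1.2, low blood pressure:* at the 1-, 2- and 5-week visits the drug is reduced or stopped for low readings, or for dizziness with orthostatic changes. The text does not say that stopping bypasses J.2.
- *I.1.2, syncope:* if "a participant reports a recent episode of syncope or loss of consciousness, study staff will also urge the participant to seek emergency medical attention". Nothing is said about the patch.
- *J.2, events during weaning:* "all study medication will be stopped while the participant receives emergency care". Whether the step-down follows afterwards is not stated.
- *J.1:* the principal investigator decides case by case whether to discontinue. How to discontinue is not covered.
- *L.3.3:* a logged exception for one participant's safety is allowed. That is an ad hoc deviation for an event J.1 already foresees.

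None of these exempts the women in question. This is a missing exception, not a contradiction between sections.

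**Who is affected**

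Syncope requires no earlier dose reduction, so a woman may be on any dose. Reason 2 requires a reduction that failed. The highest dose is 0.6 mg/hr (F.1.6), so she is then on 0.4 or 0.2.

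**Further exposure under J.2 as written**

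Nominal dose = labelled rate × 24 h, summed over the step-down days (active arm only; placebo patches deliver none).

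| Dose at stopping | Further patch-days | Nominal NTG | One full day at the dose in use | Ratio |
|---|---|---|---|---|
| 0.6 mg/hr | 2 | 0.4 × 24 + 0.2 × 24 = 9.6 + 4.8 = 14.4 mg | 0.6 × 24 = 14.4 mg | 1.0 |
| 0.4 mg/hr | 1 | 0.2 × 24 = 4.8 mg | 0.4 × 24 = 9.6 mg | 0.5 |
| 0.2 mg/hr | 0 | 0 mg | 0.2 × 24 = 4.8 mg | 0 |

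Syncope can fall in any row. Unresolved hypotension can fall only in the last two, so its maximum is 1 day at 0.2 mg/hr. With an immediate stop, every entry for further days and nominal NTG becomes 0.

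**The case against.** The strongest reply is that the text can be read so that the problem does not arise. J.1 separates discontinuing the drug from ending participation, and J.2 attaches weaning to the latter. On that reading, a woman whose drug was stopped for syncope has nothing left to wean from. She would also be sent for emergency care, where all drug is stopped, and no passage tells staff to restart it. Plasma NTG falls with a half-life of about one hour (F.1.1). Women are only asked to wean, J.2 supplies final patches only where needed, and L.3.3 permits safety exceptions. Weaning is also a deliberate trade-off against rebound, and I.1.1 expects the blood pressure effect to fade within 12 to 24 hours of continuous use.

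The reading is possible but does not settle the matter. J.1 says discontinuation usually prompts termination, and H.2.6 expressly provides weaning patches for terminations that include those made for safety. Staff reading those sections would find an instruction to taper and none to remove the patch.

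Two parts of the reply stand. The hypotension case is small, because a further reduction to 0.2 mg/hr is a step I.1.2 itself allows; syncope carries the point. And the exposure figures say nothing about the probability of harm. Each step is below the dose in use, and under H.2.5 women who escalated had acceptable blood pressure on the lower doses.

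**Conclusion.** The concern holds, as a minor participant-safety correction. As written, a woman stopped for NTG-attributed syncope has 2 further patch-days from 0.6 mg/hr, 1 from 0.4 and none from 0.2. A woman stopped for hypotension that persisted after dose reduction has at most 1, at 0.2 mg/hr.

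This assumes that staff apply J.2 and H.2.6 literally and that patches deliver their labelled rate for 24 hours. Few women are likely to be affected: I.1.1 calls hypotension severe enough to cause syncope uncommon, and reports that no pilot participant stopped for lightheadedness or hypotension. No endpoint, sample size or analysis changes.

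**What to change.** Add to J.2, with cross-references from H.2.6 and from the hypotension paragraphs of I.1.2:

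> Women discontinued for NTG-attributed syncope, or for hypotension not resolving with dose reduction, will remove the patch immediately and will not undergo step-down; for other adverse events, including significant skin reaction, the principal investigator may omit step-down if further patch use is judged unsafe. The 28-day call still applies.

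The discretion clause is included because I.1.2 also ends participation for significant skin irritation, where wearing more patches is awkward for a similar reason. Keep weaning for all other terminations, including severe hypertension, where rebound is the stated worry.

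The cost is two sentences and two cross-references, with no new procedures. The rule applies equally to active and placebo patches, so blinding is unaffected. The one downside is that these few women give up the theoretical protection against rebound chest pain and hypertension that weaning is meant to provide.
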